#### **10. EFFICACY ANALYSIS**

As one of the primary and secondary objectives of **Part B**, an efficacy evaluation with respect to ZIKV incidence will be performed. Tables providing efficacy data analysis (Table 45 through Table 56, **Appendix 1**) may be excluded if there are only a nominal number of Zika cases.

#### For primary analysis:

• **Case of ZIKV infection**: Virologically confirmed infection by PCR or other virus detection method in blood or in urine.

The final efficacy analysis will occur when the total of 90 ZIKV cases have been reported in the mITT population or following database lock and receipt of PCR or other virus detection assay results. If additional cases are reported following the data cut-off for this analysis and before the database lock, this analysis will be repeated and will include all cases reported during the study for inclusion in the final analyses.

#### For secondary analysis:

• **Subclinical case of ZIKV infection:** PCR virus detection in blood or in urine with *no* signs or symptoms. Subclinical cases of ZIKV infection will be identified by retrospective PCR or other virus testing methods.

#### For exploratory analysis:

• Symptomatic case of ZIKV infection: PCR or other virus detection method in blood or in urine in conjunction with at least one clinical sign and/or symptom.

The analyses requiring retrospective assessment of stored samples, will be conducted after database lock and Zika results are available for all subjects for inclusion in the final analysis.

For all subjects with suspected ZIKV infection a listing of all signs/and symptoms, PCR or other Zika results, and for confirmed cases, neurological symptoms, severity, and outcome are included in Listing 20 - Listing 21 for **Part B**, **Appendix 3**. Of note, Listing 18 - Listing 19 will include ZIKV data collected in **Part A**, which does not contribute to the efficacy analysis.

#### 10.1. Analysis of ZIKV Incidence

For Part B, incidence will be summarized for each ZIKV endpoint as the number and percentage of subjects along with 95% CI and be described by study group, and stratified by baseline ZIKV seroprevalence. Incidence summaries will be presented for the ITT, mITT, and PP populations, Table 45 through Table 47, Appendix 1. Incidence for each ZIKV endpoint will also be summarized in a similar presentation by clinical site Table 48 through Table 50, Appendix 1.

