#### Part B:

- To evaluate the safety and tolerability of VRC-ZKADNA090-00-VP in healthy adults and adolescents when administered IM at a dose of 4 mg by needle-free injection device compared to placebo.
- To evaluate the efficacy of VRC-ZKADNA090-00-VP by comparing incidence rates of virologic ZIKV cases in vaccine and placebo recipients.

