# 6.3.2. Sample Size Considerations: Part B

**Part B** of the study targets healthy adults and adolescents ages 15 to 35 years who reside in ZIKV endemic or potential endemic regions. This age range is considered to be the range of the highest reproductive potential and therefore, this age group will likely be the initial target for a successful ZIKV vaccine. Additionally, the risk of GBS has been shown to increase with age, so

this study population excludes those who might be at higher perceived risk for GBS [54-56]. Randomization at each study site will equally allocate subjects to vaccine or placebo schedules. The randomization plan does not include provisions for replacing subjects with incomplete product administration or visit schedules.

A total of 2400 subjects will be randomized 1:1 to receive either the study vaccine or placebo. The study sample size was determined primarily based on the evaluation of vaccine efficacy (VE). The study also has ample sample size for detecting AEs, therefore meeting the primary endpoints.

To detect a VE of 61%, the trial aims to achieve 90 cases of naturally acquired virologic ZIKV infection within 2 to 3 years. If it appears this target is unlikely to be met, the study may be expanded to achieve this target. Prior to the completion of randomization, the combined vaccine and placebo incidence rate of subclinical ZIKV cases will be calculated. At each site, the blinded site-specific baseline seropositivity rate may be calculated and used to adjust the needed sample size and to aid in allocation of enrollment slots. Both types of rates will be used to help decide if the enrollment should be extended to allow for the target to be achieved. For planning purposes, we will allow for a total sample size of up to 15,000. Such a sample size could achieve our target number of virologic ZIKV cases within 3 years, assuming full accrual within 12 months, even if the placebo incidence rate is as low as 0.50% and the seropositive rate is as high as 30% among enrollees.

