# Table 6: Probability of Observing Safety Events within a Group (n=1200)

Table 7 provides the minimum detectable difference by two-sided chi-square test between the vaccine and placebo groups over a range of possible event rates and sample sizes as follows: 1200 samples per group, 960 samples per group to account for 20% early drop out, 480 and 240 samples per group for comparisons within a stratum defined by baseline ZIKV status.

Table 7:Minimum Detectable Difference in Event Rate Assuming Type I Two-Tail
Error Rate of 5%

Sample size	Event rate	Detectable wit	th 80% power	Detectable wi	th 90% power
group (#) (in placebo) (%)		Difference (%)	Event rate (in vaccine) (%)	Difference (%)	Event rate (in vaccine) (%)
	0.1	0.81	0.91	1.04	1.14
	0.5	1.19	1.69	1.46	1.96
1200	1.0	1.50	2.50	1.80	2.80
1200	5.0	2.80	7.80	3.29	8.29
	10.0	3.69	13.69	4.32	14.32
	25.0	5.11	30.11	5.93	30.93
	0.1	0.98	1.08	1.26	1.36
	0.5	1.39	1.89	1.71	2.21
960	1.0	1.73	2.73	2.09	3.09
	5.0	3.17	8.17	3.74	8.74
	10.0	4.16	14.16	4.88	14.88
	25.0	5.73	30.73	6.66	31.66
400	0.1	1.79	1.89	2.33	2.43
	0.5	2.30	2.80	2.88	3.38
	1.0	2.75	3.75	3.38	4.38
480	5.0	4.72	9.72	5.60	10.60
	10.0	6.08	16.08	7.15	17.15
	25.0	8.20	33.20	9.55	34.55
	0.1	3.38	3.48	4.43	4.53
	0.5	3.97	4.47	5.04	5.54
240	1.0	4.54	5.54	5.65	6.65
240	5.0	7.14	12.14	8.55	13.55
	10.0	8.98	18.98	10.61	20.61
	25.0	11.79	36.79	13.73	38.73

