# 6.4.4. Analysis of ZIKV Incidence

Efficacy evaluation with respect to ZIKV incidence will be performed in **Part B**. Incidence rates for ZIKV cases will be described by vaccine group and by baseline ZIKV stratum for each group. Results will be treated both as dichotomous (infection, no infection) and as a time to event (infection) variables. The primary analysis will be based on the time to case of virologic ZIKV infection, i.e., when a subject is positive for ZIKV based on a PCR test. The time to ZIKV case data, accounting for censoring, will be described using Kaplan-Meier curves and efficacy computed using a Cox proportional hazards model. VE will be estimated by the hazard ratio from the Cox proportional hazards model stratified by baseline ZIKV exposure status.

The primary efficacy analysis is a test of the null hypothesis (H0): the study vaccine has VE no more than 20% in preventing ZIKV infection, i.e., VE  $\leq$  20%, where ZIKV infection is defined as virologically confirmed infection by PCR virus detection. The alternative hypothesis is that VE > 20%. The criterion for success will be that a one-sided test of H0 has p-value  $\leq$  0.025. This primary analysis will be based on the mITT cohort stratified by baseline serostatus (prior exposed to ZIKV or not). If the null VE  $\leq$  20% is not rejected, an additional test of H0\*: VE = 0 will be conducted using a one-sided type I error rate of 0.025.

The secondary efficacy analyses include the testing of this hypothesis over the two stratum combined. Another secondary analysis will test the above hypothesis H0, where ZIKV infection is defined as PCR virus detection irrespective of symptoms. The SAP will provide any necessary additional specificity and/or cohort definitions such as discussed at the beginning of Section 6.4.

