#### Part B

- Group 4: 4 mg ZIKVwt DNA
- Group 5: Placebo
- All Part B Subjects.

The total sample size for each summary group for the applicable analysis population being tabulated will be displayed in all tables.

All continuous variables will be summarized using the following descriptive statistics: n (nonmissing sample size), mean (or geometric mean, as appropriate), standard deviation, median, minimum and maximum. The frequency and percentages (denominators based on the non-missing sample size) of observed levels will be reported for all categorical measures. Unless otherwise specified, Clopper-Pearson exact methodology will be used to calculate CIs for proportions. All logarithmic transformations will be done using the natural log.

In presenting statistical inferences, the statistical claim (i.e. null and alternative hypotheses) will be clearly stated, the method used for hypothesis testing or CI estimation will be described and appropriately referenced, and the assumptions underlying the methods will be validated.

All data will be included in listings, sorted by study group and subject, and when appropriate by administration number and/or visit number within subject. Listings will be presented with **Part A** and **Part B** data separated.

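### The ZIKV incidence tables in SAP 10.1 give only percentages of subjects: no site-level summary allows for follow-up time, and no rate per person-year is planned

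*Combined protocol and SAP*

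**What the plan says.** The Part B efficacy objective (protocol 3.1) is to evaluate the vaccine "by comparing incidence rates of virologic ZIKV cases in vaccine and placebo recipients". Protocol 6.4.4 repeats the term: "Incidence rates for ZIKV cases will be described by vaccine group and by baseline ZIKV stratum for each group". The same section then says results will be handled both as a yes/no outcome and as time to event.

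SAP 10.1 implements the description as follows: "incidence will be summarized for each ZIKV endpoint as the number and percentage of subjects along with 95% CI", by study group and baseline serostatus in the ITT, mITT and PP populations (Tables 45-47). It adds: "Incidence for each ZIKV endpoint will also be summarized in a similar presentation by clinical site" (Tables 48-50). SAP 6.1 fixes the denominator and the interval: "The frequency and percentages (denominators based on the non-missing sample size) of observed levels will be reported for all categorical measures" and, unless otherwise specified, "Clopper-Pearson exact methodology will be used to calculate CIs for proportions". None of the six shells has a person-time column.

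SAP 10.2 uses follow-up time elsewhere. VE is one minus the Cox hazard ratio, and one-minus-Kaplan-Meier curves are drawn by arm and by arm within serostatus (Figures 27-44). None of these figures is by site.

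**The concern.** A percentage of subjects equals a risk over a stated period only if everyone is observed for that period. Several provisions allow unequal observation. The final efficacy analysis is triggered by 90 mITT cases or study completion (SAP 2.1 and 6.2). Site slots may be raised or lowered as the epidemic moves (protocol 4). Part B accrual had reached 1058 subjects about a year after it began (protocol 1.4). SAP 6.2 requires only six months of Part B follow-up for the final safety analysis.

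Tables 48-50 are the only site-level efficacy summaries, so a reader will look there for differences in transmission. A site that opened late could look like a low-transmission site. Nor can a bare percentage be set against the planning incidences in Tables 10 and 11 of the protocol, which are yearly.

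**Working it through.** **1. The plan's own figures are rates multiplied by time.** Table 10 inputs: 1200 per arm, VE 61%, accrual over 6 months, placebo incidence 2% per year. The vaccine hazard is 0.02 × 0.39 = 0.0078. Expected cases at 2 years are 1200 × the sum over arms of the mean of 1 − exp(−h·t), with t uniform from 1.5 to 2.0 years. This gives 57.5 (Table 10: 57). At 3% it gives 85.7 (Table 10: 86). The table reproduces, and it needs follow-up time to do so.

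**2. Same hazard, different follow-up.** Placebo hazard h = 0.02 per year (a Table 10 planning value), no dropout. The reported percentage is 1 − exp(−h·t). Person-years per subject are [1 − exp(−h·t)]/h, so cases over person-years equal h at every t.

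| Follow-up t | Basis | Percentage | Per 100 person-years |
|---|---|---|---|
| 0.5 years | the six months in SAP 6.2 | 1.00% | 2.00 |
| 1.04 years | assumed: entry in month 12, cut-off at 2 years | 2.06% | 2.00 |
| 1.84 years | 96 weeks = 672/365.25 | 3.61% | 2.00 |

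The largest contrast is 3.61/1.00 = 3.6-fold. It is close to the ratio of follow-up times (1.84/0.5 = 3.7), so it hardly depends on the incidence assumed.

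**3. When would follow-up be unequal at the efficacy cut-off?** The plan states that "the trial aims to achieve 90 cases of naturally acquired virologic ZIKV infection within 2 to 3 years". With 2400 subjects all followed for 96 weeks and no dropout, expected cases are:
- 2% per year: 1200 × (0.0361 + 0.0143) = about 60
- 3% per year: 1200 × (0.0537 + 0.0213) = 90
- 4% per year: 1200 × (0.0710 + 0.0283) = about 119

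At 2% the 90-case trigger is not expected before completion. At 3% the two roughly coincide. The trigger comes early only at higher incidence or with an expanded sample. The table in step 2 is therefore an illustration, not a forecast.

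**4. Everyone due to complete 96 weeks: dropout only.** The one dropout figure is in the safety power section (protocol 6.3.2.1): "960 samples per group to account for 20% early drop out". Take a constant dropout hazard L = −ln(0.8)/1.84 = 0.121. The reported percentage is h/(h+L) × [1 − exp(−(h+L)·1.84)] = 3.24%, against a 96-week risk of 3.61%; the ratio is 0.90. For assumed dropout of 5%, 10% and 30% the ratio is 0.975, 0.95 and 0.84. If all of a 20% dropout happened at once it would be 0.80.

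**5. Effect on the arm contrast in the same tables.** With 20% dropout in both arms, the vaccine percentage is 1.277% and the relative reduction is 1 − 1.277/3.240 = 60.6%, close to the true 61%. With an assumed 10% dropout in vaccine and 20% in placebo it is 1 − 1.3525/3.2404 = 58.3%.

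**The case against.** The case for leaving the tables alone is substantial.

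- **The protocol allows a yes/no summary.** Section 6.4.4 asks for it alongside the time-to-event analysis; SAP 10.1 supplies the first and 10.2 the second. This stands, so the percentages should stay. It does not supply the incidence rates that the same section calls for.
- **Censoring is already handled by arm and serostatus.** A reader might infer that the efficacy result, or the results by arm and serostatus, are left uncorrected for follow-up. The documents do not support that. Cox VE uses censored times, and Figures 27-44 give cumulative incidence for each case definition and population. What they lack is a site breakdown and a tabulated rate.
- **Unequal follow-up may not occur.** A reader might take a contrast such as 3.6% against 2.1% (1.75-fold) as what the plan implies. It does not: that contrast combines 2% per year with a 2-year cut-off, which 2400 subjects are not expected to reach (step 3).
- **Site tables are descriptive.** Data are pooled across sites (SAP 6.7), no further subgroup is powered (SAP 6.4), and randomization is 1:1 within site, so late opening does not bias the arm contrast. Blinded incidence is also monitored by site. This lowers the stakes, but a descriptive table should still describe what its title says.
- **A single rate assumes a roughly constant hazard.** In a moving epidemic, sites open at different calendar times would not be fully comparable even per person-year. This stands as a limit of the remedy.

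**Conclusion.** The point holds as a minor reporting gap. The protocol calls for incidence rates. The SAP plans percentages with binomial intervals, no rate per person-year, and no site-level summary that allows for observation time.

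The size depends on how the trial ends. With unequal follow-up, sites with the same hazard could differ up to about 3.6-fold in percentage (0.5 against 1.84 years). With full planned follow-up, the entry-time effect vanishes and only dropout remains: about 10% relative understatement at an evenly spread 20%, and 2.5% to 16% over an assumed 5% to 30%. These figures rest on constant hazards and non-informative dropout; the 20% is a safety-power allowance, not an efficacy forecast.

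Understatement here means relative to the 96-week risk. The percentage is a valid observed proportion. The primary test and its success criterion are not touched.

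**What to change.** In SAP 10.1 and Tables 45-50, add person-years at risk and cases per 100 person-years with exact Poisson 95% CIs. The site tables 48-50 matter most. Keep n and % alongside.

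Count person-time to the event, censoring or the data cut-off, from these origins:
- **ITT:** first dose.
- **mITT and PP:** one week after dose 3. These subjects are event-free until then by definition, so time from first dose would dilute the rate. With dose 3 at week 8, a hazard of 2.0 would read about 2.0 × 87/96 = 1.8 over 96 weeks, and about 2.0 × 17/26 = 1.3 over 26 weeks.

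The cost is two table columns, some SAP wording and two derivations that SAP 10.2 lacks. It measures time only from Visit 02, and it censors non-cases only at completion or termination, dates that a subject still in follow-up at the 90th case will not have. State beside the tables that the rate summarises well only if the hazard is roughly constant. No new data are needed.

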#### **10.2.** Analysis of vaccine efficacy:

The time of ZIKV events is defined as the illness onset date recorded on the ZIKV Endpoints eCRF (for clinical cases) or date first specimen was collected with a positive PCR or other Zika result, whichever is earliest. Time to event for analysis will be as follows:

- For subjects with infection: time of ZIKV event minus date of first administration (Visit 02) + 1.
- For subjects with no infection: date of protocol completion/termination as recorded on the study status eCRF minus date of first administration (Visit 02) + 1. These subjects will be censored at their date of study completion or date of early termination.
- Subjects with or without infection may be censored from the analysis for the PP population as described in Section 6.3.

For subjects who were randomized but did not receive any product, date of randomization will be used in place of date of first administration in the definitions above.

The cumulative incidence of ZIKV cases will be presented graphically as 1 – Kaplan-Meier curves. Curves will be presented by study group and baseline ZIKV stratum and by study group combined over all subjects (Figure 27 through Figure 44, Appendix 2). Similar presentations will be displayed for virologic ZIKV cases and subclinical ZIKV cases).

Vaccine efficacy will be estimated as 1 - Hazard Ratio estimated from a Cox proportional hazard model. The primary efficacy analysis for ZIKV infection will use the following test:

H0: VE 
$$\leq 20\%$$
  
H1: VE  $\geq 20\%$ 

The criterion for success will be that a one-sided test of  $H_0$  has p-value  $\leq 0.025$ . Success will be met if the lower bound of the 95.0% confidence interval for VE estimated for the mITT population using a Cox proportional hazards model stratified by baseline ZIKV status is >20 (Table 51 through Table 53, Appendix 1).

If the null hypothesis VE  $\leq 20\%$  is not rejected, then the following will be tested using a one-sided type I error rate of 0.025.

H\*0: VE =0% H\*1: VE >0%

As secondary analyses of vaccine efficacy this hypothesis will be tested for:

- ZIKV cases without stratification for baseline ZIKV serostatus
- virologic ZIKV cases stratified by baseline ZIKV serostatus
- subclinical ZIKV cases stratified by baseline ZIKV serostatus
- subclinical ZIKV cases without stratification for baseline ZIKV serostatus

All analyses will be included in Table 51 through Table 53, Appendix 1. All efficacy analyses will be conducted for ITT, mITT, and PP populations. For all analyses the assumptions of proportional hazards and non-informative censoring will be evaluated.

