## 4.2.7. Pregnancy during the Study

Female subjects of childbearing potential will receive pregnancy prevention counseling throughout the study. Women will be asked to notify the site immediately if they suspect or learn they are pregnant during this study. In case of pregnancy, subjects will be removed from the product administration schedule but may have limited clinic contacts and blood draws at the discretion of the site PI and IND Sponsor.

Each site will have a prepared list of resources for any woman who becomes pregnant during the study. Sites will also refer pregnant women to the CDC guidance on how to protect themselves from getting ZIKV infection (https://www.cdc.gov/zika/pregnancy/protect-yourself.html).

All pregnancies that begin during the study will be recorded. The site must contact the subject to learn the outcome of a pregnancy that begins during the study.

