## 4.3. Evaluation of ZIKV Infection During the Study

## 4.3.1. ZIKV Infection Definition

A virologic case of ZIKV infection will be defined as a virologically confirmed ZIKV infection irrespective of symptoms.

A subclinical case of ZIKV infection will be defined as a virologically confirmed ZIKV infection without clinical signs or symptoms of ZIKV. Subclinical cases of ZIKV infection will be identified by retrospective PCR testing of stored whole blood samples.

A symptomatic case of ZIKV infection will be defined as a virologically confirmed ZIKV infection in conjunction with at least one clinical sign and/or symptom. According to the CDC, the most common symptoms of ZIKV are fever, rash, joint pain, or conjunctivitis (red eyes). Other common symptoms include muscle pain and headache.

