## 4.3.2. Unscheduled Collection of Samples for Suspected ZIKV Infection

At any time during the study, if a subject exhibits any sign or symptom possibly consistent with a ZIKV infection, PI or designee must attempt to diagnose the infection rapidly. PCR testing must be used to test for ZIKV infection because vaccine-induced antibodies could be detected by antibody-based diagnostic tests and even mimic the antibody profile of acute or remote ZIKV infection.

Sample collection for diagnostic testing may occur during a scheduled study visit or an unscheduled visit may be conducted. All samples sent to the PDL will be tested using the RealStar® Zika Virus RT-PCR to test for ZIKV specific RNA. Upon site request, the PDL will also run the TrioPlex Real-time RT-PCR for the differentiation of ZIKV, DENV and CHIKV RNA. The site should request TrioPlex when there is suspicion of DENV and/or CHIKV based on clinical symptoms or local epidemiology in order to differentiate from ZIKV infection.

Because diagnostic testing based on ZIKV-specific antibody tests could lead to inadvertent unblinding, study staff will remind subjects that it is preferable that no testing for ZIKV infection be done outside of the trial during study participation unless required to provide care to the subject, such as if needed while traveling. If this occurs, virologic (PCR-only) test results should be provided to the study team as available so that proper documentation of ZIKV infection can occur. In addition to laboratory testing, subjects should always be evaluated using clinical judgment, local requirements, and the current CDC or WHO definitions of ZIKV infection: https://wwwn.cdc.gov/nndss/conditions/zika-virus-disease-and-zika-virus-congenital-infection/case-definition/2016/ or http://www.who.int/csr/disease/zika/case-definition/en/respectively.

In **Part A**, diagnostic testing of suspected ZIKV infections by virus detection (e.g., PCR) may be done through the PDL or by the site's local standard testing procedures. It is recommended that serum and urine be collected for laboratory testing but there is no requirement for the type or number of samples that should be collected and tested. Note that only samples collected on one day are recorded in the database if collected, additional samples must be recorded and tracked in the subject study file.

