## 4.5.1. Discontinuation from Receiving Study Product

Subjects who receive at least one product administration are expected to continue with planned follow-up visits until the end of the study. If the second product administration is not given, then the subject should be discontinued from the third product administration.

A subject may be discontinued from getting study product for the following reasons:

- Pregnancy;
- Grade 3 AE assessed as related to study product (except that self-limited Grade 3 solicited reactogenicity does not require discontinuation of product administrations);
- Grade 4 AE assessed as related to study product;
- Immediate hypersensitivity reaction associated with study product;
- Confirmed ZIKV infection;
- Clinically significant intercurrent illness that is not expected to resolve before the next scheduled product administration;
- Treatment with systemic glucocorticoids (e.g., prednisone or other glucocorticoid) or other immunomodulators (other than nonsteroidal anti-inflammatory drugs [NSAIDs]), with the exception that study product administration may continue per site PI discretion if the next one occurs at least 2 weeks following completion of glucocorticoid treatment; or,
• The IND Sponsor and/or PI assess that it is not in the best interest of the subject to continue receiving study product.

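### SAP 10.2 censors uninfected subjects at the study-status date instead of the last PCR-tested sample, so terminal time without scheduled sampling counts as infection-free

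*Combined protocol and SAP*

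**What the plan says.** **Endpoint.** Protocol 4.3.1 says a virologic case "will be defined as a virologically confirmed ZIKV infection irrespective of symptoms". The same section says how silent infections are found: "Subclinical cases of ZIKV infection will be identified by retrospective PCR testing of stored whole blood samples".

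**Event time.** SAP 10.2 uses illness onset or the "date first specimen was collected with a positive PCR or other Zika result, whichever is earliest".

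**Censoring time.** For subjects without infection, SAP 10.2 uses "date of protocol completion/termination as recorded on the study status eCRF minus date of first administration (Visit 02) + 1", and adds: "These subjects will be censored at their date of study completion or date of early termination". Neither document mentions the last sample in this context, or says how the termination date is set for a subject lost to follow-up.

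**Sampling.** Part B blood is drawn every 4 weeks to Week 48 and every 8 weeks after that (Protocol 4.2.6 and Appendix III, Table C). Symptom-triggered PCR runs alongside: "At any time during the study, if a subject exhibits any sign or symptom possibly consistent with a ZIKV infection", the site must try to diagnose it rapidly (Protocol 4.3.2).

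**Who stays in follow-up.** Protocol 4.5.1: "Subjects who receive at least one product administration are expected to continue with planned follow-up visits until the end of the study". Pregnant subjects stop product and "may have limited clinic contacts and blood draws at the discretion of the site PI and IND Sponsor" (Protocol 4.2.7).

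**The concern.** Event dates come from specimens or illness; censoring dates come from an administrative form. The two fit together only if sampling continues up to the form date. Protocol 1.1 says most infected people never show symptoms, so once scheduled sampling stops, most infections could not be recorded, yet the subject stays in the Cox and Kaplan-Meier risk sets.

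Three routes lead into such time:
- A subject lost to follow-up, whose status date may be later than the last sample. This is the strongest case.
- A subject who stops attending but is not yet terminated; Protocol 4.5.2 makes termination optional.
- A pregnant subject with fewer draws. Contraception is required only to 12 weeks after the last dose, that is Week 8 + 12 = Week 20 of 96.

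At stake are the cumulative-incidence curves in both arms and, if unsampled time differs by arm, the hazard ratio of the primary test.

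**Working it through.** **1. The plan's own figure.** No stated figure depends on the censoring date. The power statement (90 cases, VE 61%, null VE of at most 20%, 90% power; Protocol 6.3.2.3) conditions on the case count. With p0 = 4/9 and p1 = 0.39/1.39 = 0.281, the normal approximation gives 90.2% at 90 cases, which agrees. The point concerns estimation, not the power calculation.

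**2. Inputs.** From the documents: 96 weeks of follow-up, 1:1 allocation, VE of 61% or 20%, placebo incidence of 3% per year (one of the Table 10 scenarios), and 20% dropout (given only for the safety comparison, Protocol 6.3.2.1). Assumed, because the documents are silent: the gap L from last sample to status date (8 weeks, 26 weeks, or running to Week 96), dropout by arm (10% to 30%), and no detection at all within the gap.

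**3. Share of the true hazard observed.** Let dropout be exponential with total proportion d by Week 96, and k = -ln(1-d)/96 per week. The fraction of the risk set still under sampling is exp(-kt) for t < L and exp(-kL) afterwards. Averaged over follow-up:

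r(d, L) = [(1 - exp(-kL))/k + (96 - L)·exp(-kL)] / 96

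For d = 20%, 96k = 0.223:
- L = 8: r = 0.982, so the rate is understated by 1.8%
- L = 26: r = 0.949, understated by 5.1%
- to Week 96: r = 0.2/0.223 = 0.896, understated by 10.4%

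At 3% per year the true placebo cumulative incidence at Week 96 is 1 - exp(-0.0552) = 5.37%. Multiplying the exponent by r gives 5.28%, 5.10% and 4.83%, which are relative understatements of about 2%, 5% and 10%.

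**4. Effect on VE.** Approximately, observed HR = true HR × r(vaccine)/r(placebo). Example: 20% vaccine and 10% placebo dropout, gap to Week 96: 0.39 × 0.896/0.949 = 0.368, so VE reads 63.2%.

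A Cox simulation (6,000 per arm, 200 replicates, placebo hazard 3% per year) analysed the same data under both rules. VE in percent, last-sample rule → status-date rule:

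| True VE | Dropout vaccine/placebo | 8-week gap | 26-week gap | Gap to Week 96 |
|---|---|---|---|---|
| 61 | 20/20 | 61.3 → 61.3 | 61.2 → 61.2 | 61.2 → 61.1 |
| 61 | 20/10 | 61.1 → 61.4 | 60.8 → 61.8 | 61.1 → 63.3 |
| 61 | 10/20 | 60.9 → 60.5 | 61.0 → 59.9 | 61.3 → 58.9 |
| 61 | 30/10 | 61.8 → 62.6 | 60.8 → 63.0 | 60.7 → 65.2 |
| 20 | 20/20 | 19.4 → 19.4 | 19.8 → 19.8 | 19.4 → 19.4 |
| 20 | 20/10 | 19.4 → 20.1 | 21.2 → 23.3 | 19.8 → 24.3 |
| 20 | 30/10 | 18.6 → 20.2 | 20.2 → 24.7 | 19.8 → 29.0 |

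The last-sample values scatter around the truth by simulation error, so the within-cell difference is the quantity to read. With equal dropout it is at most 0.1 point. More unsampled time on vaccine raises VE; more on placebo lowers it. Because the effect multiplies the HR, the shift at true VE 20% is about 0.80/0.39 = 2 times that at 61%.

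**The case against.** Several stronger readings are tempting, and the documents do not support them.

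- *That nobody was testing these subjects.* Symptom-triggered PCR continues for anyone on study, pregnant subjects may still be bled, and formally withdrawn subjects leave the risk set at termination, normally adding about one visit interval (4 to 8 weeks). Completers have whole blood taken at Week 96, so their last sample and completion date normally coincide. What is lost is asymptomatic detection, mainly in the three groups named.
- *That lost or pregnant subjects necessarily stay at risk to Week 96.* SAP 10.2 uses the recorded termination date, and no text says how it is set. Long gaps are possible, not documented.
- *That Protocol 4.2.7 contradicts 4.5.1.* One is a specific pregnancy provision, the other a general expectation.
- *That all incidence outputs are biased.* SAP 10.1 reports numbers and percentages of subjects, so the censoring date does not enter.
- *That the 20% dropout is unsampled person-time.* It is a safety sample-size allowance.
- *That VE is inflated.* Part B is blinded and 1:1, and nothing in the documents shows unsampled time differing by arm.

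It is also fair that earlier gaps may be partly covered by a later draw, since Protocol 1.1 cites RNA in red cells for up to 154 days. The SAP will also evaluate non-informative censoring (10.2) and may impute (6.5), and Protocol 6.4 mentions inverse propensity weighting. These are relevant safeguards, but none moves the censoring date.

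Finally, a bare last-sample rule has its own flaw. A symptom-triggered case after the last scheduled draw would count, while event-free subjects under the same surveillance would already be censored, which slightly overstates incidence. That objection stands and shapes the fix.

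**Conclusion.** The gap is real and worth closing, but modest. Terminal time without scheduled sampling is treated as infection-free for an endpoint that includes asymptomatic infection. Kaplan-Meier cumulative incidence is understated by about 2% to 10% (relative) at an assumed 20% dropout, with gaps from 8 weeks to Week 96.

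VE is essentially unchanged if unsampled time is equal by arm. With 20%/10% dropout and gaps of 8 to 26 weeks it shifts by about 0.3 to 1 point at true VE 61%, and 0.7 to 2.1 points at true VE 20%. Larger shifts, such as 9 points at the null boundary, need 30%/10% dropout with the gap running to Week 96.

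Gaps and arm-specific dropout are assumptions. Treating the gap as wholly untested makes these figures upper-end for subjects still on study, because symptom-triggered PCR would detect some cases. This is a low-cost improvement to the analysis rule, not a threat to the trial's validity.

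**What to change.** In SAP 10.2:

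1. For the virologic and subclinical endpoints, censor subjects without infection at the collection date of their last evaluable PCR-tested sample, scheduled or symptom-triggered, in ITT, mITT and PP.
2. State how a symptom-triggered event arising after a long sampling gap is handled, so that cases and non-cases under the same surveillance are treated alike.
3. Define the date for subjects lost to follow-up as last contact or last sample, and say which applies to which analysis.
4. Keep status-date (or last-contact) censoring for the symptomatic-case analysis, where symptom surveillance is the relevant exposure, and as a sensitivity analysis for the primary endpoint.
5. Report terminal unsampled time (status date minus last tested sample) by arm, so a reader can see whether any imbalance could matter.

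Cost: a few SAP sentences, one derived date and one summary table. Specimen dates are already needed to date events, and the efficacy database locks separately after laboratory data arrive (SAP 2.1). The downside is a small loss of person-time covered only by symptom surveillance. No change to visits, sampling or the management of pregnant subjects is needed.
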